10.1.5.3 Time at Risk in the post-COVID-19 pandemic period

Subjects with study drug period continuing after the COVID-19 pandemic periods will have a time at risk calculated during that period:

- For subjects with date of last dose of study drug on or after the end date of the COVID-19 pandemic period, minimum between:
date of last dose + 141 - maximum of (COVID-19 pandemic end date, date of first dose)
date of last clinical contact - maximum of (COVID-19 pandemic end date, date of first dose) +1
- For subjects who have died on or after *COVID-19 pandemic end date*:
Date of death - maximum of (COVID-19 pandemic end date, date of first dose) + 1 (If the date of death is later than 140 days following the last dose of BKZ, this rule does not apply).
- For subjects with date of last dose of study drug on or before *COVID-19 pandemic end date* but with the earliest date between (date of last dose + 141) and (date of last clinical contact) on or after *COVID-19 pandemic end date*, minimum between :
date of last dose + 141 - COVID-19 pandemic end date
date of last clinical contact - COVID-19 pandemic end date+1

10.2 Adverse events

An AE is any untoward medical occurrence in a patient or clinical investigation subject administered a pharmaceutical product that does not necessarily have a causal relationship with this treatment. An AE can therefore be any unfavorable and unintended sign (including an abnormal laboratory finding), symptom, or disease temporally associated with the use of a medicinal (investigational) product, whether related or not to the IMP.

AEs (including SAEs) are characterized as either non-treatment or treatment-emergent according to the following criteria:

- Non treatment-emergent are the events with onset date and time prior to the very first administration of study medication (BKZ or placebo) or after a 140-day period after the final drug administration.
- Treatment-emergent AEs (TEAE) are those with onset date at or after the very first administration of study medication. The events that emerge within 140 days after the final drug administration, will also be considered as treatment-emergent (eg, in the case of premature discontinuation or during the SFU Period).

If an AE occurs on the same day as the treatment switch (Week 16, to BKZ for subjects randomized to Placebo) then the AE will be allocated to the Double-Blind Treatment. An exception from this general rule is made for the following types of AEs that will be allocated to the BKZ:

- Events that fulfill the anaphylaxis criteria for acute events (refer to Appendix 1)
- Events that fulfill the hypersensitivity reaction criteria (refer to Appendix 1)
- Events with a high-level term (HLT) of “Administration site reactions NEC”
- Events with an HLT of “Injection site reactions”

The incidence of TEAEs will be summarized descriptively by treatment group, MedDRA primary system organ class (SOC), HLT, and preferred term (PT).

AEs will be presented as “number of subjects (percentage of subjects) [number of events]”. In this style of output, “[number of events]” will include all cases of an AE including repeat occurrences in individual subjects, while “number of subjects” will count each subject only once.

Adverse event summaries by SOC, HLT and PT will be ordered alphabetically for SOC and HLT within SOC and in terms of decreasing frequency for PT within HLT in the BKZ treatment group and then similarly by decreasing frequency in the placebo group.

AE summaries by PT will be ordered in terms of decreasing frequency for PT within the BKZ treatment group, and in the event of ties, PT will be sorted alphabetically.

TEAEs will be classified by period (DBP, ATP or AMP) according to their date of emergence.

Summary tables of TEAEs will be provided on:

- The DBP by treatment on the SS,
- The ATP by treatment and for all BKZ-treated subjects in the ATS,
- The AMP for all BKZ-treated subjects and the ADA group in the AMS.

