2.3 Study design and conduct

2.3.1 Study description

This is a Phase 3, multicenter, randomized, double-blind, placebo-controlled, noninferiority active reference study to evaluate the efficacy and safety of BKZ in subjects with active PsA who are biologic disease-modifying antirheumatic drug (bDMARD) naive. To be eligible to participate in this study, subjects must be adults with a diagnosis of active PsA based on the Classification Criteria for Psoriatic Arthritis (CASPAR) and have disease with TJC ≥ 3 and SJC ≥ 3 . In addition, subjects should not have been previously exposed to any bDMARD for PsA or PSO to be eligible for the study.

Approximately 840 subjects will be randomly assigned in a 3:2:1 ratio, stratified by region (North America, Western Europe, Eastern Europe, and Asia/Australia) and bone erosion (0, ≥ 1) to 1 of the 3 following blinded treatment groups:

- Bimekizumab 160mg sc Q4W (420 subjects),
- Placebo (280 subjects),
- Adalimumab sc 40mg every 2 weeks (Q2W) (140 subjects).

It is planned to enroll a minimum of 45% of subjects who have elevated hs-CRP (≥ 6 mg/L) and/or who have at least 1 bone erosion at Screening.

[figure not shown]
The overall study design consists of:

- a Screening Period (≥ 14 days to ≤ 35 days)
- a 16-week placebo controlled Double-Blind Treatment Period (DBP)
- a 36-week Active Treatment-Blind Period (ATP) (Week 16 to week 52)
- a Safety Follow Up (SFU) visit, 20 weeks after the final dose of IMP (for subjects not entering the open label extension (OLE) study or who discontinue early, including those withdrawn from IMP, as applicable).

The maximum study duration per subject will be up to 73 weeks.

The study schematic diagram for the study is presented in.

Figure 2-1: Study schematic diagram

ACR50=American College of Rheumatology 50% response criteria, BKZ=bimekizumab, PsA=psoriatic arthritis; Q2W=every 2 weeks, Q4W=every 4 weeks, sc=subcutaneous, SFU=Safety Follow-Up, W=week

^a Adalimumab dosing is performed every 2 weeks from Baseline to Week 50.

^b After 16 weeks of double-blind treatment, subjects will enter the Active Treatment-Blind Period. All subjects randomized to placebo will be reallocated to receive BKZ 160mg Q4W. Subjects randomized to BKZ 160mg Q4W will continue to receive their originally randomized dose. Subjects randomized to active reference (ADA) will continue with their active treatment.

^c Permitted rescue therapy is defined in Protocol Section 5.4.

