3.6.5 Active Medication Set

The Active Medication Set (AMS) will consist of all subjects who have received at least 1 dose of active IMP (BKZ or ADA). The AMS will cover the analysis of data collected during the Active Medication Periods (AMP), ie:

- The ATP for subjects randomized to placebo,
- The DBP and the ATP for subjects randomized to BKZ or ADA.

The AMS will be used for summaries of safety during the AMP.

The anti-BKZ antibody will also be analyzed on the AMS for subjects receiving BKZ.

In this analysis set, the order of the treatment groups presented in tables from left to right will be:

- BKZ Total (all BKZ treated subjects)
- ADA 40mg Q2W.

For the analysis of the compliance, study medication and time at risk, the order of the treatment groups to be presented in tables from left to right will be:

- Placebo / BKZ 160mg Q4W
- BKZ 160mg Q4W
- BKZ 160mg Q4W Total (all BKZ treated subjects)
- ADA 40mg Q2W.

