10.2.1 Standard AE summaries

Tables for incidence of the following categories of TEAES will be provided:

- TEAEs (overview),
- TEAEs by SOC, HLT, PT,
- TEAEs by decreasing frequency of PT,
- TEAEs above the reporting threshold of 5% by PT, by SOC and PT
- TEAEs by maximum intensity,
- TEAEs by relationship to IMP,
- Related TEAEs by SOC, HLT, PT,
- Related TEAEs above the reporting threshold of 5% by PT, by SOC and PT
- TEAEs leading to study discontinuation, by SOC, HLT, PT,

- TEAEs leading to study drug discontinuation, by SOC, HLT, PT,
- Treatment-emergent SAEs (TESAEs) by SOC, HLT, PT,
- TESAEs by relationship by SOC, HLT, PT,
- TEAEs leading to Death by SOC, HLT, PT - Deaths will also be tabulated and listed,
- Non-serious TEAEs above the reporting threshold of 5% of subjects by relationship by PT.

Some selected tables of incidence will include the exposure adjusted incidence rate (EAIR) with associated 95% CI and the exposure adjusted event rate (EAER) ([Section 10.2.3](#)). The categories of TEAES concerned are listed below:

- TEAEs by SOC, HLT, PT,
- TEAEs leading to study discontinuation by SOC, HLT, PT,
- TEAEs leading to study drug discontinuation,
- TEAEs by timing of onset relative to ADAb status by SOC, HLT, PT (on subjects treated with BKZ). This will include columns for the following:
 - TEAEs starting before the first ADAb positive result (includes ADAb categories 2 and 5) where TEAEs have occurred before the following events: a) the first positive ADAb result for subjects in category 2 and b) the first post-baseline boosted ADAb titer result for subjects with titer results and the first post-Baseline positive ADAb result for subjects with positive ADAb at Baseline with no other samples with titer available for subjects in category 5.
 - TEAEs starting on the same date or after the first ADAb positive result (includes ADAb Categories 2, 3, 4, 5 and 6) where TEAEs have occurred on or after the following events: a) the first positive ADAb results for subjects in categories 2, 3, 4 and 6, and b) the first post-baseline boosted ADAb titer result for subjects with titer results and the first post-Baseline positive ADAb result for subjects with positive ADAb at Baseline with no other samples with titer available for subjects in category 5.
 - TEAEs for subjects who are ADAb negative at all timepoints (includes ADAb Category 1).

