The below results will be presented on the SS (for the DBP), on the ATS (for the ATP by treatment and for all BKZ-treated subjects), and on the AMS (for all the BKZ-treated subjects and on the ADA group). All values observed at any time while on treatment (ie, occurring at scheduled and unscheduled visits) will be included in the below tables. Baseline values and values observed more than 140 days after the last administration of study medication are not considered:

- Number and percentage of subjects with treatment-emergent markedly abnormal laboratory data overall (for blood chemistry and hematology), All values observed at any time while on treatment (ie, occurring at scheduled and unscheduled visits) will be included in this table summarizing markedly abnormal values. For this summary, Baseline values and values observed more than 140 days after the last administration of study medication are not considered.
- Number and percentage of subjects with markedly abnormal liver enzyme elevation tests (data beyond the CTCAE Grade 3 thresholds as outlined in [Table 10-5](#))

All laboratory data will be listed by treatment, subject and visit including changes from Baseline for numeric variables, flags for measurements outside the normal ranges, the relative study day, a flag for whether the test was not done and a flag for whether the subject was fasting.

The markedly abnormal laboratory data will also be listed separately.

Listings will also include Hepatitis B and C, human immunodeficiency virus (HIV), genomic proteomic/metabolomics, and genetic/epigenetic tests.

In addition, the laboratory results classified as Grade 3 or Grade 4 will be listed separately.

Urinalysis laboratory results and hepatic events will be listed separately.

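### AMP harm tables set BKZ Total, with a shorter planned window, beside ADA and omit the randomised BKZ column that has ADA's window

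*SAP*

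**What the plan says.** Section 3.6.5 defines the AMP differently by randomised arm: "The ATP for subjects randomized to placebo", but "The DBP and the ATP for subjects randomized to BKZ or ADA". Its default layout for the Active Medication Set (AMS) has two columns, BKZ Total and ADA. Section 10.2 applies that layout to adverse events ("The AMP for all BKZ-treated subjects and the ADA group in the AMS"). Section 10.3 applies it to markedly abnormal laboratory and liver values ("on the AMS (for all the BKZ-treated subjects and on the ADA group"), and Section 10.4.1 to markedly abnormal blood pressure. Table 4-4 confirms the two columns for AEs, safety topics and markedly abnormal values.

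For AMS compliance, study medication and time at risk, Section 3.6.5 uses four columns instead: Placebo/BKZ, BKZ 160mg Q4W, BKZ Total and ADA.

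Section 10.2 reports AEs as numbers and percentages of subjects, with event counts. Section 10.2.1 then limits exposure adjustment: "Some selected tables of incidence will include the exposure adjusted incidence rate (EAIR". The listed tables are TEAEs by SOC/HLT/PT, TEAEs leading to study or drug discontinuation, serious TEAEs, and the antibody-status tables. Section 10.2.4 adds EAIR and EAER to the safety topics.

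**The concern.** Two adjacent columns invite a direct reading. Here they cover different planned lengths of follow-up, and the difference always runs the same way, because only the BKZ column contains subjects who enter at Week 16. The randomised BKZ arm, which has the same planned window as ADA, does not appear in these tables.

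A reader cannot rebuild the missing figure from the other AE tables. Each subject is counted once per table, so the double-blind (DBP) and active-treatment (ATP) percentages cannot be added into a Day 1 to Week 52 incidence without double counting.

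What is at stake is the crude picture of harm with BKZ relative to ADA. TEAE incidence is a secondary safety variable (Section 2.2.5.1).

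**Working it through.** **Inputs.** Section 2.3.1 gives the allocation ("Approximately 840 subjects will be randomly assigned in a 3:2:1 ratio"), the arm sizes, a 16-week DBP and a 36-week ATP. Section 3.6.5 gives the AMP definition. The SAP states no event rates and no figure for this imbalance, so the risks below are illustrative.

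**Arm sizes.** 840 × 3/6 = 420 BKZ, 840 × 2/6 = 280 placebo and 840 × 1/6 = 140 ADA, as the SAP states.

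**Share of switchers in BKZ Total.** 280/(420 + 280) = 40.0%. If 5%, 10% or 15% of placebo subjects leave before receiving BKZ (assumed range), the share is 266/686 = 38.8%, 252/672 = 37.5% or 238/658 = 36.2%.

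**Mean planned window at Week 52.** BKZ Total: (420 × 52 + 280 × 36)/700 = 45.6 weeks. ADA: 52 weeks. The ratio is 45.6/52 = 0.877.

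**Effect on crude percentages.** Assume the same constant hazard on BKZ and ADA, no dropout, and no safety follow-up time. For a 52-week incidence p:
- ADA and randomised BKZ both show p.
- Switchers show 1 − (1 − p)^(36/52).
- BKZ Total shows 0.6p + 0.4 × [1 − (1 − p)^(36/52)].

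| ADA and randomised BKZ | Switchers | BKZ Total | Gap (points) | Relative |
|---|---|---|---|---|
| 5% | 3.5% | 4.4% | 0.6 | 12% |
| 20% | 14.3% | 17.7% | 2.3 | 11% |
| 60% | 47.0% | 54.8% | 5.2 | 9% |

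With 10% placebo dropout before Week 16, the result barely moves: a 10% ADA risk shows as 8.9% in BKZ Total instead of 8.8%.

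**Week 24 analysis.** Section 10.2.5 limits AEs to onset before Week 24. The windows are then 24 weeks, and 8 weeks for switchers: (420 × 24 + 280 × 8)/700 = 17.6 against 24 weeks, and a 10% ADA risk shows as 7.4%. Section 4.3.1 and Table 4-4 instead run the safety tables to a cut-off date set by the last subject's Week 24 visit. That would lengthen follow-up and reduce the gap, so the Week 24 figure holds only under the Section 10.2.5 rule.

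**Where the gap is unadjusted.** EAIR and EAER are not listed for the overview, maximum intensity, relationship, 5%-threshold and death tables, nor for markedly abnormal laboratory, liver and blood pressure values.

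**The case against.** The case on the other side is substantial, and most of it stands.

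- *Randomised BKZ is shown beside ADA elsewhere.* The DBP and ATP tables of AEs and markedly abnormal values each have it as a separate column over a common window (Section 10.2, Table 4-4). Over the whole study, Section 10.3 gives CTCAE grades, liver thresholds and Hy's Law cases by randomised group. Table 4-4 does the same for by-visit vital signs, ECG and eC-SSRS. A reader might infer that the AMP tables are the only 52-week safety display with ADA, or that the randomised arm is hidden throughout. The SAP supports neither.
- *Exposure adjustment covers the main tables.* It accompanies the main TEAE, serious TEAE, discontinuation and safety-topic tables, and AMS time at risk is tabulated by arm, so the unequal follow-up is disclosed. The offset is not exact as worded: Section 10.2.3 starts the clock for subjects with an event at first IMP dose, and Section 3.3 bases first dose on the first injection, active or not. Read literally, switchers with events would add 16 placebo weeks. At equal hazard, BKZ Total's EAIR would be 0.99 of ADA's at a 10% 52-week risk and 0.93 at 50%.
- *A shortfall in every crude percentage does not follow.* For reactions clustered soon after the first active dose, the switchers' risk period lies inside their window and the deficit shrinks. Safety follow-up of subjects not entering the extension also moves actual windows away from 36 and 52 weeks.
- *The gap is often small against noise.* One ADA subject is 1/140 = 0.7 points, more than the 0.6-point gap at 5%. At 20% the ADA standard error is √(0.2 × 0.8/140) = 3.4 points, against a gap of 2.3.
- *No BKZ–ADA safety contrast is planned.* The risk difference in Section 10.2.4.9 is BKZ minus placebo in the DBP. Pooling all BKZ exposure is also a legitimate way to describe overall harm.

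What the objection leaves unanswered is the absence of a cumulative Day 1 to Week 52 column for randomised BKZ in the AMP harm tables. Section 10.2.5 acknowledges unequal exposure only between subjects in safety follow-up and those entering the extension, not for Week 16 switchers.

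**Conclusion.** The point holds for the AMP tables of adverse events, safety topics, markedly abnormal laboratory values and blood pressure, and not beyond them. BKZ Total has a mean planned window of 45.6 weeks beside 52 for ADA. Where only crude percentages are given, it is understated relative to ADA by about 9 to 12% at Week 52. This rests on an equal, constant hazard, all 280 placebo subjects switching, and no follow-up beyond Week 52. It is less for early-onset events, and slightly less if placebo subjects drop out before Week 16.

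A reader might infer that these tables bias a test of BKZ against ADA. They do not: the AMP tables are descriptive and the testing hierarchy is BKZ against placebo. Nor are the switchers simply non-randomised, since they were randomised to a planned placebo-then-BKZ sequence and selection enters only through losses before Week 16. This is an inexpensive improvement to presentation, with no effect on the efficacy conclusions.

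**What to change.** In Sections 3.6.5, 10.2, 10.2.4, 10.3, 10.4.1 and Table 4-4, add the column BKZ 160mg Q4W (randomised, Day 1 to Week 52) to the AMP harm tables, next to BKZ Total and ADA. Section 3.6.5 already defines this column for AMS exposure and compliance. State that it is the column with the same planned window as ADA, and footnote that BKZ Total has a shorter planned window because placebo switchers enter at Week 16. Under the equal-hazard assumption above, the randomised BKZ and ADA percentages then agree by construction.

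The cost is SAP wording, a table-shell update and wider tables. No new data or analysis method is needed.

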10.2.1 Standard AE summaries

Tables for incidence of the following categories of TEAES will be provided:

- TEAEs (overview),
- TEAEs by SOC, HLT, PT,
- TEAEs by decreasing frequency of PT,
- TEAEs above the reporting threshold of 5% by PT, by SOC and PT
- TEAEs by maximum intensity,
- TEAEs by relationship to IMP,
- Related TEAEs by SOC, HLT, PT,
- Related TEAEs above the reporting threshold of 5% by PT, by SOC and PT
- TEAEs leading to study discontinuation, by SOC, HLT, PT,

- TEAEs leading to study drug discontinuation, by SOC, HLT, PT,
- Treatment-emergent SAEs (TESAEs) by SOC, HLT, PT,
- TESAEs by relationship by SOC, HLT, PT,
- TEAEs leading to Death by SOC, HLT, PT - Deaths will also be tabulated and listed,
- Non-serious TEAEs above the reporting threshold of 5% of subjects by relationship by PT.

Some selected tables of incidence will include the exposure adjusted incidence rate (EAIR) with associated 95% CI and the exposure adjusted event rate (EAER) ([Section 10.2.3](#)). The categories of TEAES concerned are listed below:

- TEAEs by SOC, HLT, PT,
- TEAEs leading to study discontinuation by SOC, HLT, PT,
- TEAEs leading to study drug discontinuation,
- TEAEs by timing of onset relative to ADAb status by SOC, HLT, PT (on subjects treated with BKZ). This will include columns for the following:
 - TEAEs starting before the first ADAb positive result (includes ADAb categories 2 and 5) where TEAEs have occurred before the following events: a) the first positive ADAb result for subjects in category 2 and b) the first post-baseline boosted ADAb titer result for subjects with titer results and the first post-Baseline positive ADAb result for subjects with positive ADAb at Baseline with no other samples with titer available for subjects in category 5.
 - TEAEs starting on the same date or after the first ADAb positive result (includes ADAb Categories 2, 3, 4, 5 and 6) where TEAEs have occurred on or after the following events: a) the first positive ADAb results for subjects in categories 2, 3, 4 and 6, and b) the first post-baseline boosted ADAb titer result for subjects with titer results and the first post-Baseline positive ADAb result for subjects with positive ADAb at Baseline with no other samples with titer available for subjects in category 5.
 - TEAEs for subjects who are ADAb negative at all timepoints (includes ADAb Category 1).
- TEAEs by NAb status (ADAb negative, NAb positive, ADAb positive / NAb, negative) on subjects treated with BKZ. TEAEs will be sorted by system organ class, high level term and preferred term.
Note: for TEAE by onset relative to ADAb positivity and by NAb status, all available ADAb and NAb data at the time of IA cut-off, respectively, will be utilized to derive the subject-level ADAb/NAb status categories.
- TESAEs by SOC, HLT, PT.

By-subject listings on all AEs and all deaths will be provided on the Enrolled Set. AEs leading to study discontinuation will also be listed on the SS. AE occurring at first study drug administration (including for subjects randomized to Placebo, at first administration of BKZ at Week 16) will also be listed. A glossary listing will also be created for all TEAEs.

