- From Week 24 visit, if the ADA_b sample is collected within ±21 days relative to the visit date at which the drug was administered (or ±21 days from a scheduled visit at which dosing was not performed), the ADA_b result for that sample will be associated with the scheduled visit and summarized accordingly.
- In all cases, this will include unscheduled assessments as described in [Section 3.1](#) (if a dose was administered at an unscheduled visit). Samples collected outside this window will be excluded from the ADA_b summaries and will be listed only.

The rules above will apply to by-visit summaries only. This rule will not apply for the Week 52, ET or SFU visits. Thus, all ADA_b data obtained at these visits will be included in the by-visit summaries.

All other summaries of ADA_b status will use all available data (scheduled and unscheduled).

In addition, the anti-BKZ antibody status will be further classified according to the ADA_b categories outlined below:

- **Category 1: Pre ADA_b negative – treatment-emergent ADA_b negative:** Includes subjects who are negative at Baseline and antibody negative at all sampling points post treatment (including SFU), one post-baseline missing/inconclusive sample is allowed for subjects with pre-ADA_b negative sample. This group also includes subjects who have missing/inconclusive pre-treatment sample (eg either missing/inconclusive or insufficient volume) at baseline with all post-baseline samples as ADA_b negative.
- **Category 2: Pre ADA_b negative – treatment-emergent ADA_b positive:** Includes subjects who are negative at Baseline and antibody positive at any sampling point post treatment (including SFU). This group also includes subjects who have a missing pre-treatment sample (either missing or insufficient volume) at Baseline with one or more ADA_b positive post-treatment samples.

- **Category 3: Pre ADA_b positive – treatment reduced ADA_b:** Includes subjects who are positive at Baseline, and antibody negative at all sampling points post treatment (including SFU).

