- **Category 4: Pre ADA_b positive – treatment unaffected ADA_b positive:** Includes subjects who are positive at Baseline and are positive at any sampling point post treatment (including SFU) with titer values of the same magnitude as Baseline (ie less than a predefined fold difference from the Baseline value). For the purposes of this study, this is set at an increase of less than the validated Minimum Significant Ratio (MSR) of 2.07-fold from baseline.
- **Category 5: Pre ADA_b positive – treatment boosted ADA_b positive:** Includes subjects who are positive at Baseline and are positive at any sampling point post treatment (including SFU) with increased titer values compared to Baseline (greater than or equal to a predefined fold difference increase from Baseline value which is defined within the validation of the assay). For the purposes of this study, this is set at an increase greater than or equal to the validated Minimum Significant Ratio (MSR) of 2.07-fold from Baseline.

Note: For any subject who is positive at Baseline and positive at a post-Baseline time point, but for whom titers are not available to determine treatment unaffected or treatment boosted status, the subject will be considered as treatment boosted (ie, Category 5), assuming no other samples are available.

- **Category 6: Inconclusive:** Includes subjects who have a positive pre-treatment sample and some post-treatment samples are missing, while other post-treatment samples are ADA_b negative or missing.
- **Category 7: Total treatment-emergent:** Category 2 and 5 combined: Includes subjects who are pre ADA_b negative – treatment emergent ADA_b positive (Category 2) and pre ADA_b positive – treatment boosted ADA_b positive (Category 5).
- **Category 8: Total prevalence of pre-ADA_b positivity:** (Categories 3, 4, 5 and 6 combined): Subjects that are tested ADA_b positive at Baseline.
- **Category 9: Missing:** Includes subjects who have a negative or a missing/inconclusive pre-treatment sample and some post-treatment samples are missing/inconclusive, while other post-treatment samples are ADA_b negative or missing.

For the subjects randomized to placebo group, the Baseline will be the Week 16 pre-dose observation.

All the following analyses will be prepared on the SS on BKZ treated subjects by treatment group (Placebo / BKZ 160mg Q4W and BKZ 160mg Q4W):

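### The table of adverse events by onset relative to anti-bimekizumab antibody uses two different clocks for subjects who are already antibody positive at Baseline

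*SAP*

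**What the plan says.** Section 10.2.1 (Standard AE summaries) plans a table of TEAEs by onset relative to ADAb status in bimekizumab-treated subjects, with EAIR, its 95% CI, and EAER. It has three columns.

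- Earlier column: "TEAEs starting before the first ADAb positive result (includes ADAb categories 2 and 5").
- Later column: "TEAEs starting on the same date or after the first ADAb positive result (includes ADAb Categories 2, 3, 4, 5 and 6").
- A column for category 1, subjects who are never positive.

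The same section fixes the dividing date by category. In the later column it is "a) the first positive ADAb results for subjects in categories 2, 3, 4 and 6". For category 5, in both columns, it is "the first post-baseline boosted ADAb titer result for subjects with titer results", or the first post-Baseline positive if no titers exist.

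Section 9.2.1 defines the categories.

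- Category 2 is negative at Baseline and positive later.
- Category 3: "Includes subjects who are positive at Baseline, and antibody negative at all sampling points post treatment (including SFU").
- Category 4 is positive at Baseline and afterwards, "with titer values of the same magnitude as Baseline (ie less than a predefined fold difference from the Baseline value").
- Category 5: "Includes subjects who are positive at Baseline and are positive at any sampling point post treatment (including SFU) with increased titer values compared to Baseline", the threshold being 2.07-fold.
- Category 6 is positive at Baseline, with later samples negative or missing.
- Category 7, total treatment-emergent, is "Category 2 and 5 combined: Includes subjects who are pre"-negative subjects who turn positive, together with Baseline-positive subjects who are boosted.
- Category 8 confirms that categories 3, 4, 5 and 6 together make up the Baseline-positive subjects.

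**The concern.** Both column titles refer to the first positive result. For anyone positive at Baseline that result precedes all treatment, so no TEAE can come before it. The rule respects this for categories 3, 4 and 6 and departs from it for category 5. Two Baseline-positive subjects with the same early event can therefore land in opposite columns, depending only on a titer measured later.

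This is the only table in the SAP that relates the onset of adverse events to the timing of antibody. Because it carries incidence rates with confidence intervals, readers will compare the columns. If the columns mix two definitions, a difference between them, or its absence, cannot be read cleanly as an effect of antibody formation.

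**Working it through.** **Allocation under the stated rule.** Take TEAEs on days 10 and 100, and assume the first post-Baseline positive (category 2) or boosted titer (category 5) falls on day 56.

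| Category | Baseline ADAb | Clock starts | Day 10 | Day 100 | Day 10 by the column title |
|---|---|---|---|---|---|
| 2 | negative | day 56 | before | after | before |
| 3 | positive | Baseline | after | after | after |
| 4 | positive | Baseline | after | after | after |
| 5 | positive | day 56 | **before** | after | **after** |
| 6 | positive | Baseline | after | after | after |

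Category 2 is a true before/after split. Category 5 before the boost contradicts the column title.

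**Can one reading repair both columns?**

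- If the clock is first positivity, categories 3, 4 and 6 are placed correctly, but category 5 has no place in the earlier column.
- If the clock is treatment-emergent antibody (category 7, that is 2 and 5), the category 5 anchor is right, but categories 3, 4 and 6 have no place in the later column.

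Neither reading makes the table consistent.

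**Stability.** A note in section 10.2.1 derives the categories for this table from all antibody data available at the cut-off, and section 10.2.5 has the TEAE tables rerun at Week 52. A category 4 subject at Week 24 who is boosted afterwards becomes category 5, and an unchanged early TEAE moves from 'after' to 'before'.

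**Size, on assumed inputs.** The SAP gives no category frequencies. Assume, per 100 bimekizumab subjects, 30 in category 2 and 2 in category 5, each with first positive or boost at Week 12 of 52, and 12 in categories 3, 4 and 6 combined. Let the background TEAE rate be 1 and the rate after antibody formation be 2, with follow-up divided at the same dates as the events.

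- 'After' follow-up from categories 2 and 5: (30 + 2) × 40 = 1,280 subject-weeks.
- 'After' follow-up from categories 3, 4 and 6: 12 × 52 = 624, which is 624/1,904 = 33% of the column.

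With the 'before' column at the background rate, the observed ratio is:

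- all 12 at the background rate: (2 × 1,280 + 624)/1,904 = 1.67;
- half in category 4 at the raised rate, half at background: (2,560 + 624 + 312)/1,904 = 1.84;
- all 12 in category 4 at the raised rate: (2,560 + 1,248)/1,904 = 2.00.

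In the 'before' column, category 5 supplies 2 × 12 = 24 of 32 × 12 = 384 subject-weeks, about 6%. If those weeks also carried the raised rate, the 'before' rate would be (360 + 48)/384 = 1.06, and each ratio above would fall by about 6%.

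**The case against.** The strongest defence is that the rule is explicit. Every category has a stated anchor, so the table can be reproduced and a careful reader can see what was counted. The category 5 anchor also follows a convention used elsewhere: the first-occurrence table in section 9.2.1 counts the first boosted result for category 5, and merges that category with category 2 when it holds under 10% of subjects. The table is described as relative to ADAb status, not treatment-emergent ADAb, so placing categories 3, 4 and 6 in 'after' is literally true. On this view only the category 5 label is wrong, and a footnote would do. Other outputs also bear on the question: a TEAE table by neutralizing-antibody status, a column for never-positive subjects, and full listings.

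Much of this stands. The rule is reproducible and the table is descriptive, with no test or decision attached. But a footnote would correct only the label. The later column would still combine time since Baseline positivity in some subjects with time since a boost in others. The neutralizing-antibody table classifies subjects by overall status and does not address timing.

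A reader might also infer that boosted subjects sit wholly in 'before', or that the table contains no valid before/after contrast. Neither is so. Category 5 appears in both columns, with only its events up to the anchor in the earlier one, and the category 2 split is valid.

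**Conclusion.** The defect is real and limited. In one descriptive safety table, Baseline-positive subjects are divided by two incompatible clocks, and category 5 events before the boost appear under a title that is false for them. Efficacy testing is not affected.

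The size is unknown. The range of 1.67 to 2.00 for a true ratio of 2 rests wholly on assumed frequencies, an assumed Week 12 onset, and a 'before' column at the background rate. Its upper end is no attenuation at all, and the effect is small if Baseline positivity is rare.

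It is tempting to conclude that both features pull the columns together and so hide a safety signal. The document does not support that as a general claim. For categories 4 and 5, dilution of 'after' by unboosted category 4 subjects requires that unboosted Baseline antibody carries no extra risk, while contamination of 'before' by category 5 requires that it does. The direction therefore depends on facts the SAP does not give. Severity: low.

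**What to change.** In section 10.2.1, limit the before and after columns to categories 2 and 5, which is the SAP's own category 7. Title them as before, and on or after, the first treatment-emergent or boosted ADAb result. Keep the existing anchor dates for these two categories. Show TEAEs for categories 3, 4 and 6 (ADAb positive at Baseline, not boosted) in a separate column, and leave the category 1 column as it is.

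The cost is a change of SAP wording and one more table column. No new data are needed and no events are lost. The downside is that the 'after' column holds fewer events, so its rates are less precise.
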